1.3. Sample Size and Power

Due to the exploratory nature of this study, no formal power calculations were used to determine sample size. The sample size was selected based on practical reasons.

With a sample size of 80, the 95% confidence interval will extend at most 23% in length.

2. TYPE OF PLANNED ANALYSIS

2.1. Data Monitoring Committee

This study does not have a Data Monitoring Committee.

2.2. Final Analysis

After all subjects have completed the study, outstanding data queries have been resolved, and the database has been cleaned and finalized, the final analysis of the data will be performed.

3. GENERAL CONSIDERATIONS FOR DATA ANALYSES

Analysis results will be presented using descriptive statistics. For categorical variables, the number and percentage of subjects in each category will be presented; for continuous variables, the number of subjects [n], mean, standard deviation [SD], median, first quartile [Q1], third quartile [Q3], minimum, and maximum will be presented.

Data collected in the study will be presented in by-subject listings for all subjects in the Safety Analysis Set, unless otherwise specified. All by-subject listings will be presented by subject identification (ID) number in ascending order, unless otherwise specified.

3.1. Analysis Sets

Analysis sets define the subjects to be included in an analysis. Analysis sets and their definitions are provided in this section. The number of subjects eligible for each analysis set will be provided. Subjects who were excluded from each analysis set will be summarized or provided in a by-subject listing with reasons for exclusion.

3.1.1. All Enrolled Analysis Set

The All Enrolled Analysis Set includes all subjects who were enrolled into the study. Subjects will be grouped by assigned treatment at enrollment (ie, SOF/VEL 12 Weeks).

3.1.2. Full Analysis Set

The Full Analysis Set (FAS) includes all enrolled subjects who took at least 1 dose of the study drug. Since all subjects in this study were assigned to and received SOF/VEL for 12 Weeks, the FAS will be the same as the Safety Analysis Set.

This is the primary analysis set for efficacy analyses.

3.1.3. Safety Analysis Set

The Safety Analysis Set includes all subjects who took at least 1 dose of the study drug. Subjects are grouped within the Safety Analysis Set according to the treatment they actually received.

This is the primary analysis set for safety analyses.

3.1.4. Pharmacokinetic Analysis Set

The Pharmacokinetic (PK) Analysis Set includes all subjects who took at least 1 dose of the study drug and have at least 1 nonmissing postdose concentration value for the corresponding analyte in plasma. The analytes of interest may include SOF and its metabolites GS-566500 and GS-331007, and VEL. The PK analysis set will be used for analyses of population PK. Subjects will be grouped according to the treatment they actually received.

3.2. Subject Grouping

The treatment group for all subjects will be “SOF/VEL 12 Weeks”.

In general, the efficacy analyses will be performed for the FAS overall and by HCV genotype (1 total [and further broken down for 1a and 1b], 2, 3, 4, 5, and 6). The primary analysis will be performed for the “SOF/VEL 12 Weeks” group as described in Section 6.1. HCV genotype will be determined by Covance laboratories using the LiPA 2.0 assay or by Sanger NS5B population sequencing when results from LiPA 2.0 are unsuccessful, "indeterminate", or resulted in "mixed genotype" and to determine genotype 1 subtype if it is not reported.

The safety analyses will be performed for “SOF/VEL 12 Weeks” using the Safety Analysis Set.

3.3. Strata and Covariates

There are no strata or covariates for this study.

3.4. Examination of Subject Subsets

Subject subsets will be explored overall and by HCV genotype (1 total [and further broken down by 1a, 1b], 2, 3, 4, 5, and 6) for the primary efficacy endpoint, SVR12, including the following:

- age (< 65 years, \geq 65 years)
- sex at birth (male, female)
- race (white, black, all other races)
- ethnicity (Hispanic or Latino, non-Hispanic or Latino)
- baseline BMI (< 30 kg/m², \geq 30 kg/m²)
- cirrhosis (no, yes)
- baseline HCV RNA (< 800,000 IU/mL, \geq 800,000 IU/mL)
- baseline alanine aminotransferase (ALT) (\leq 1.5 \times upper limit of normal [ULN], $>$ 1.5 \times ULN)

- IL28B (CC, non-CC; with non-CC further broken down to CT, TT)
- prior HCV treatment (treatment naive, treatment-experienced)
- prior HCV treatment experience and cirrhosis status (ie, treatment naive with cirrhosis, treatment-experienced with cirrhosis, treatment naive without cirrhosis, treatment-experienced without cirrhosis)

3.5. Multiple Comparisons

No multiplicity adjustment will be made since SVR12 is the primary efficacy endpoint.

3.6. Missing Data and Outliers

3.6.1. Missing Data

In general, missing data will not be imputed unless methods for handling missing data are specified.

For subjects with a missing last dose date of study drug, imputation rules are described in Section 3.8.1. The handling of missing or incomplete dates for adverse event (AE) onset is described in Section 7.1.5.2, and for prior and concomitant medications in Section 7.4.

For analyses of categorical HCV RNA data, missing posttreatment HCV RNA data will have the missing data imputed. Missing on-treatment HCV RNA will have missing data imputed up to the time of the last dose (for on-treatment displays). If the study day associated with the last dosing date of any study drug is greater than or equal to the lower bound of a visit window, and the value at the visit is missing, then the value will be imputed. If the study day associated with the last dosing date is less than the lower bound of a visit window then the on-treatment value at that visit will remain missing.

If an HCV RNA data point is missing and is preceded and followed in time by values that are “< LLOQ target not detected (TND),” then the missing data point will be set to “< LLOQ TND.” If a data point is missing and preceded and followed by values that are “< LLOQ detected,” or preceded by “< LLOQ detected” and followed by “< LLOQ TND,” or preceded by “< LLOQ TND” and followed by “< LLOQ detected,” then the missing value will be set to “< LLOQ detected.” In these situations the data point will be termed a bracketed success; otherwise, the data point will be termed a bracketed failure (ie, \geq LLOQ detected). If a data point is missing and is not bracketed, the missing data point will also be termed a failure (ie, \geq LLOQ detected).

For the analyses of continuous HCV RNA efficacy data, when and only when a missing HCV RNA value is imputed as < LLOQ TND or < LLOQ detected according to the imputation rules described above, will the corresponding continuous value be imputed to LLOQ – 1 IU/mL. No other imputation will be performed for continuous HCV RNA data.

3.6.2. Outliers

Outliers will be identified during the data management and data analysis process, but no sensitivity analyses will be conducted. All data will be included in the data analysis.

3.7. Data Handling Conventions and Transformations

By-subject listings will be presented for all subjects in the Safety Analysis Set sorted by subject ID number, visit date, and time (if applicable) unless otherwise specified. Data collected on log forms, such as AEs, will be presented in chronological order for each subject.

Age (in years) on the date of the first dose of study drug and sex at birth will be used for analyses and presentation in listings.

If a subject was not dosed with study drug at all, then the date the informed consent was signed will be used in place of the first dose date of study drug for calculations. For some countries, only birth year is collected on the eCRF. In those cases, “01 January” will be used for the unknown birth day and month for the purpose of age calculation, unless age is captured on the CRF.

Non-PK data that are continuous in nature but are less than the lower limit of quantitation (LLOQ) or above the upper limit of quantitation will be imputed as follows:

- A value that is one unit less than the limit of quantitation will be used for calculation of descriptive statistics if the datum is reported in the form of “< x” (where x is considered the limit of quantitation). For example, if the values are reported as < 50 and < 5.0, values of 49 and 4.9, respectively, will be used for calculation of summary statistics. An exception for this rule is any value reported < 1. For the values reported as < 1 or < 0.1, value of 0.9 or 0.09 will be used for calculation of summary statistics.
- A value that is one unit above the limit of quantitation will be used for calculation of descriptive statistics if the datum is reported in the form of “> x” (where x is considered the limit of quantitation). Values with decimal points will follow the same logic as above.
- The limit of quantitation will be used for calculation of descriptive statistics if the datum is reported in the form of “≤ x” or “≥ x” (where x is considered the limit of quantitation).

The COBAS® AmpliPrep/COBAS® TaqMan® HCV Quantitative Test, version 2.0 was used to determine HCV RNA results in this study. The LLOQ of the assay is 15 IU/mL.

When the calculated HCV RNA IU/mL is within the linear range of the assay, then the result will be reported as the “<< numeric value>> IU/mL.” This result will be referred to in this document as the numeric result or as “ \geq LLOQ detected” for the categorical result.

When HCV RNA is not detected, the result is reported as “No HCV RNA detected” or “target not detected”. This result will be referred to in this document as “ $<$ LLOQ target not detected” or “ $<$ LLOQ TND.”

When the HCV RNA IU/mL is less than LLOQ of the assay, the result is reported as “ < 15 IU/mL HCV RNA detected.” This result will be referred to in this document as “ $<$ LLOQ detected.”

The overall category of HCV RNA $<$ LLOQ includes “ $<$ LLOQ TND” and “ $<$ LLOQ detected.”

For numerical HCV RNA data, values below LLOQ will be set to the LLOQ – 1 IU/mL (ie, 14 HCV RNA IU/mL). HCV RNA values returned as “target not detected” will also be set to LLOQ – 1 IU/mL.

If methods based on the assumption that the data are normally distributed are not adequate, analyses may be performed on transformed data (eg, \log_{10} scale) or nonparametric analysis methods may be used, as appropriate.

3.8. Visit Windows

3.8.1. Definition of Study Day

Study day is the day relative to the date of the first dose of study drug. Study Day 1 will be defined as the day of first dose of study drug administration.

Study day will be calculated from the date of first dose of study drug administration and derived as follows:

- For postdose study days: Assessment Date – First Dose Date + 1
- For days prior to the first dose: Assessment Date – First Dose Date

The last dose date for the study drug will be the end date on study drug administration eCRF for the record where the “subject permanently discontinued” flag is ‘Yes’.

If there are subjects for whom the date of last study drug is unknown due to the reason that the subject was lost to follow-up and not able to be contacted, the date of last dose will be estimated using the maximum of nonmissing study drug start or stop dates, visit dates, and laboratory collection dates (posttreatment visits and unscheduled visits are not included).

3.8.2. Analysis Windows

Subject visits might not occur on protocol-specified days. Therefore, for the purpose of analysis, observations will be assigned to analysis windows.

In general, the baseline value will be the last nonmissing value on or prior to the first dose date of study drug.

HCV RNA, vital signs, and safety laboratory data collected up to the last dose date + 3 days are considered to be on-treatment data and HCV RNA, vital signs, and safety laboratory data collected after the last dose date + 3 days are considered posttreatment data. The analysis windows for on-treatment HCV RNA, vital signs and safety laboratory data are provided in [Table 3-1](#).

Table 3-1. Analysis Windows for On-treatment HCV RNA, Vital Signs and Safety Laboratory Data

Nominal Visit	(SOF/VEL 12 Weeks)		
	Nominal Day	Lower Limit	Upper Limit
Baseline ^a	1	(none)	1
Week 2	14	2	21
Week 4	28	22	42
Week 8	56	43	70
Week 12 ^a	84	71	≥ 85

a Coagulation and urinalysis tests will only be collected at baseline and Week 12.

HCV RNA, vital sign, and safety laboratory data collected after the last dose date + 3 days will be assigned to a posttreatment follow-up (FU) visit. Visit windows will be calculated from the last dose date (ie, FU Day = collection date minus the last dose date) as shown in [Table 3-2](#).

Table 3-2. Analysis Windows for Posttreatment HCV RNA, Vital Signs and Hematology/Chemistry Safety Laboratory Data

Nominal FU ^a Visit	HCV RNA			Vital Signs and Safety Laboratory Data ^b		
	Nominal FU Day	Lower Limit	Upper Limit	Nominal FU Day	Lower Limit	Upper Limit
FU-4	28	21	69	28	4	30
FU-12	84	70	146		NA	

a FU-x visit = posttreatment Week-x follow-up visit.

b Vital signs and hematology/chemistry safety labs will only be summarized for the FU-4 visit (up to 30 days after last dose). Coagulation and urinalysis tests are not collected at posttreatment visits.

ECG data collected at the screening visit will be listed using the nominal visit.

3.8.3. Selection of Data in the Event of Multiple Records in an Analysis Window

Depending on the statistical analysis method, single values may be required for each analysis window. For example, change from baseline by visit usually requires a single value, whereas a time-to-event analysis would not require 1 value per analysis window.

If multiple valid nonmissing numeric observations exist in an analysis window, records will be chosen based on the following rules if a single value is needed:

- For baseline, the last available record on or prior to the date of the first dose of study drug will be selected. If there are multiple records with the same time or no time recorded on the same day, the average (arithmetic mean) will be used for the baseline value.
- For postbaseline visits:
 - The record closest to the nominal day for that visit will be selected except for HCV RNA posttreatment follow-up visits, for which the latest record in the analysis window will be selected.
 - If there are 2 records that are equidistant from the nominal day, the later record will be selected.
 - If there is more than 1 record on the selected day, the average will be taken, unless otherwise specified.
- If multiple valid nonmissing categorical observations exist in a window, records will be selected as follows:
 - For baseline, the last available record on or prior to the date of the first dose of study drug will be selected. If there are multiple records with the same time or no time recorded on the same day, the value with the lowest severity will be selected (eg, normal will be selected over abnormal). If multiple ECG measurements occur on the same day prior to the first dose of any study drug, the value with the lowest severity will be selected regardless of the timing of these multiple ECG measurements.
 - For postbaseline visits, follow the same rules described above for postbaseline numeric observations, except that if there are multiple records on the same day, the most conservative value will be selected (eg, abnormal will be selected over normal).

4. SUBJECT DISPOSITION

4.1. Subject Enrollment, Screen Failures, and Disposition

4.1.1. Subject Enrollment

A summary of subjects enrolled and treated will be provided for each country and investigator within country for the “SOF/VEL 12 Weeks” group for subjects in the safety analysis set.

4.1.2. Screen Failures

Reasons for screen failure will be summarized for each screen that was performed for the study. The total number of screens and number of screen failures will be provided. Screen failures will be split into the following 2 groups:

Percentages will be calculated for the screen failure rate (denominator is number of screens), each inclusion/exclusion criteria not met (denominator is screen fails that did not meet criteria), and reasons for non-enrollment (denominator is screen fails that met eligibility criteria). A listing of reasons for screen failure will be provided, sorted by screening IDs for subjects who were screened but not treated.

4.1.3. Subject Disposition

The summary of subject disposition will be provided for “SOF/VEL 12 Weeks”. The summary will present the number of subjects enrolled, and the number of subjects in each of the categories listed below.

- Treated (Safety Analysis Set)
- In FAS
- In PK Analysis Set
- Completed study treatment
- Did not complete study treatment with reasons for premature discontinuation of study treatment
- Completed study
- Did not complete the study with reasons for premature discontinuation of study

For the percentage of subjects who completed or did not complete study treatment or study, the denominator for the percentage calculation will be the total number of subjects in the Safety Analysis Set. Among subjects who completed study treatment and who discontinued study treatment, the number and percentage of subjects will be summarized for the following:

- Who had no HCV posttreatment Week 4 assessment and thereafter (No HCV FU-4 and thereafter)
- Who had HCV posttreatment Week 4 assessment but no HCV posttreatment Week 12 and thereafter (With HCV FU-4 but No FU-12 and thereafter)

If a subject did not have any HCV RNA assessment \geq 21 days after the last dose of any study drug (ie, lower bound of FU-4 visit for HCV RNA data), the subject is categorized as having “No HCV FU-4 and thereafter.” If a subject had the HCV FU-4 assessment but did not have any HCV RNA assessment \geq 70 days after the last dose of any study drug (ie, lower bound of FU-12 visit for HCV RNA data), the subject is categorized as having “With HCV FU-4 but No FU-12 and thereafter.”

In addition, the total number of subjects who were screened, enrolled, and the number of subjects in each of the disposition categories listed above will be depicted by a flowchart.

The following by-subject listings will be provided by subject identification (ID) number in ascending order to support the above summary tables:

- Disposition for subjects who complete study treatment and study
- Disposition for subjects who did not complete study treatment and/or study with reasons for premature discontinuation of study treatment and/or study
- Lot number(s)

4.2. Extent of Exposure

Extent of exposure to study drug will be examined by assessing the total duration of study drug exposure and the level of adherence to the study drug regimen specified in the protocol.

4.2.1. Duration of Exposure to Study Drug

Total duration of exposure to study drug will be defined as last dose date minus first dose date plus 1, regardless of any temporary interruptions in study drug administration, and will be expressed in weeks (ie, total duration [in days] divided by 7) using up to 1 decimal place (eg, 4.5 weeks).

The total duration of exposure to study drug (ie, weeks) will be summarized using descriptive statistics (n, mean, SD, median, Q1, Q3, minimum, and maximum) and using the number (ie, cumulative counts) and percentage of subjects exposed through the following time periods: Baseline (Day 1), Week 2 (Day 14), Week 4 (Day 28), Week 8 (Day 56), and Week 12 (Day 84).

A 3-day window is applied to the last planned on-treatment visit to match with the protocol-specified visit window. A summary will be provided for the “SOF/VEL 12 Weeks” group for the Safety Analysis Set.

4.2.2. Adherence to Study Drug

The total number of tablets administered will be summarized using descriptive statistics (n, mean, SD, median, Q1, Q3, minimum, and maximum).

The presumed total number of tablets administered to a subject will be determined by the data collected on the drug accountability eCRF using the following formula:

$$\begin{aligned} \text{Total Number of Doses Administered} = \\ (\sum \text{No. of Tablets Dispensed}) - (\sum \text{No. of Tablets Not Administered}) \end{aligned}$$

The level of adherence to the study drug will be assessed based on the total amount of study drug administered relative to the total amount of study drug prescribed at baseline.

The level of adherence will be expressed in percentage using the following formula:

$$\text{Level of Adherence}(\%) = \left(\frac{\text{Total Amount of Study Drug Administered}}{\text{Total Amount of Study Drug Prescribed at Baseline}} \right) \times 100$$

Note: If calculated adherence is greater than 100%, the result will be set to 100%.

In this study, the total amount of SOF/VEL (400/100 mg) prescribed for 12 weeks would require 84 tablets.

Subjects who prematurely discontinue study drug for lack of efficacy (ie, virologic failure) will have the total amount of study drug prescribed calculated up to the first date when virologic failure criteria were met. For virologic failure confirmed by 2 consecutive measurements, the date of the first measurement will be used. If study drug bottles are dispensed on or after the date that the subject first met virologic failure criteria, these bottles will not be included in the calculation of adherence. If a bottle is dispensed and the bottle is returned empty, then the number of tablets returned will be entered as zero. If a bottle is dispensed but not returned (missing), the number of tablets taken from that bottle will be counted as zero.

Descriptive statistics for the level of adherence (n, mean, SD, median, Q1, Q3, minimum, and maximum) with the number and percentage of subjects belonging to adherence categories (eg, < 80%, ≥ 80 to < 90%, ≥ 90%) will be provided for the “SOF/VEL 12 Weeks” group for the Safety Analysis Set. No inferential statistics will be provided.

A separate by-subject listing of study drug administration and drug accountability will be provided by subject ID number (in ascending order) and visit (in chronological order).

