#### **3.3. HCV Virologic Response-Based Stopping Criteria**

The following on-treatment HCV virologic response-based treatment stopping criteria will be utilized for all subjects:

- Confirmed HCV RNA  $\geq$ LLOQ after 2 consecutive HCV RNA <LLOQ

- Confirmed  $>1 \log_{10}$  increase from nadir
- HCV RNA  $\geq$ LLOQ through 12 weeks of treatment

Confirmation should be performed as soon as possible but within 2 weeks after determination of initial observation indicating virologic failure.

If HCV viral relapse is detected at post-treatment Week 4 or 12 visits, subjects will be asked to return for a confirmatory visit.

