## 5.6. Study Drug Accountability

The investigator is responsible for ensuring adequate accountability of all used and unused study drug (SOF/VEL FDC). This includes acknowledgement of receipt of each shipment of study drugs (quantity and condition). All used and unused study drugs dispensed to subjects must be returned to the site.

SOF/VEL FDC accountability records will be provided to each study site:

- Record the date received and quantity of study drug bottles
- Record the date, subject number, subject initials, the study drug bottle number dispensed
- Record the date, quantity of used and unused study drug returned, along with the initials of the person recording the information.

- At the Baseline/Day 1 visit, subjects will be dispensed 2 bottles of SOF/VEL so that they have sufficient tablets to cover the 3 day time window around the Week 4 and Week 8 visit. Subjects must be instructed to bring back the study drug in the original container at every post Day 1 study visit through the end of study treatment. The extra bottle dispensed at Baseline/Day 1 visit must be brought back to each on-treatment visit for accountability purposes and will be re-dispensed to the subject except at Week 12 or EOT visit.

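### For subjects stopped early for virologic failure, the SAP adherence ratio cuts prescribed tablets at the first failing sample but can still count tablets taken after it

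*SAP*

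**What the plan says.** SAP 4.2.2 defines adherence as tablets administered over tablets prescribed. Tablets administered are the sum dispensed minus the sum not administered. A full 12-week course is 84 tablets.

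Subjects who stop early for virologic failure have a special denominator. They "will have the total amount of study drug prescribed calculated up to the first date when virologic failure criteria were met". Where failure needs confirming, the earlier sample sets the date: "For virologic failure confirmed by 2 consecutive measurements, the date of the first measurement will be used".

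The only related limit on the numerator works by bottle: "If study drug bottles are dispensed on or after the date that the subject first met virologic failure criteria, these bottles will not be included". The SAP also applies a cap: "If calculated adherence is greater than 100%, the result will be set to 100" per cent. A bottle that is never returned counts as zero tablets taken.

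On supply, Protocol 5.6 states: "At the Baseline/Day 1 visit, subjects will be dispensed 2 bottles of SOF/VEL". Protocol 5.2.2 gives 28 tablets per bottle. The extra bottle is brought to each on-treatment visit and re-dispensed, except at Week 12 or end of treatment.

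On timing, Protocol 3.3 makes breakthrough and rebound stopping criteria only once confirmed: "Confirmation should be performed as soon as possible but within 2 weeks after determination of initial observation indicating virologic failure".

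**The concern.** The two terms of the ratio can cover different periods. The denominator ends at the first failing sample. The numerator continues for as long as the subject draws on bottles issued before that date. Each such tablet adds to the top and nothing to the bottom, and the cap hides any ratio that passes 100%.

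At stake is how one failure reads in the report. A subject who missed many doses before failing could be placed in the 90% or above category instead of below 80%. That would make a failure after poor tablet-taking look like a failure despite good tablet-taking.

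**Working it through.** **The plan's own figure.** 12 weeks × 7 days × 1 tablet per day = 84 tablets, which matches SAP 4.2.2.

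**Inputs.**
- P, tablets prescribed up to first failure: 28 at Week 4 and 56 at Week 8 (one tablet daily).
- t, tablets taken up to first failure: chosen for illustration.
- d, tablets taken afterwards from bottles dispensed earlier, at one per day. Assumed range 0 to 14. The 2 weeks in Protocol 3.3 run from determination of the result, so a longer interval is possible.
- Supply from earlier bottles: 2 × 28 = 56 tablets at a Week 4 failure. At Week 8 it is 84, assuming one more bottle at Week 4; Protocol 6.2.3 leaves the number to the IWRS.

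**Formulas.** SAP rule: min(100%, (t + d)/P). Both terms cut at failure: t/P. Both terms to last dose: (t + d)/(P + d).

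| Failure | t | d | SAP rule | Both cut at failure | Both to last dose |
|---|---|---|---|---|---|
| Week 8, P = 56 | 40 | 14 | 54/56 = 96.4% | 40/56 = 71.4% | 54/70 = 77.1% |
| Week 8 | 40 | 7 | 47/56 = 83.9% | 71.4% | 47/63 = 74.6% |
| Week 8 | 40 | 0 | 71.4% | 71.4% | 71.4% |
| Week 4, P = 28 | 18 | 14 | 32/28 = 114.3%, shown as 100% | 18/28 = 64.3% | 32/42 = 76.2% |
| Week 4 | 18 | 7 | 25/28 = 89.3% | 64.3% | 25/35 = 71.4% |

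Before the cap, the overstatement against t/P is d/P: 14/56 = 25 points at Week 8 and 14/28 = 50 points at Week 4.

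**Lowest adherence to failure still reported as 90% or more.** With d = 14: 37/56 = 66.1% at Week 8 and 12/28 = 42.9% at Week 4. With d = 7: 44/56 = 78.6% and 19/28 = 67.9%. Leaving the failure day out of the prescribed count (P = 55 or 27) moves these by about 2 points or less.

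**If the re-dispensed extra bottle is excluded.** At Week 8, the first bottle and the Week 4 bottle hold 56 tablets. With 40 taken, 16 remain, enough for 14 more, so 96.4% stands. At Week 4, the first bottle has 28 − 18 = 10 left, so the most that can be counted is 28/28 = 100% (against 28/38 = 73.7% with both terms to last dose). The ratio then cannot exceed 100%, but 64.3% is still reported as 100%. Both results need the opened bottle to stay with the subject and be used after the failing visit.

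**Which failures qualify.** On-treatment samples are scheduled at Weeks 2, 4, 8 and 12. Breakthrough needs two consecutive results below LLOQ first, so on scheduled samples it cannot appear before Week 8. A Week 4 case must be rebound. Nonresponse through Week 12 comes when treatment is complete, so it is not a premature stop.

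**How many subjects.** In the four completed phase 3 studies in Protocol 1.2.2.1, the SOF/VEL 12-week groups total 624 + 134 + 277 + 90 = 1,125. No listed discontinuation in these groups was for virologic failure, and the genotype 3 study, which does not itemise its two, had no on-treatment virologic failure. The exact two-sided 95% upper limit for 0/1,125 is 1 − 0.025^(1/1125) = 0.33%, or about 0.26 subjects in 80. The decompensated-cirrhosis study had 2 breakthroughs in 267, both in other arms; that rate gives 80 × 2/267 = 0.6. Neither population is this one.

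**Effect on the group mean.** One subject moving from 71.4% to 96.4% shifts a mean over 80 subjects by 25/80 = 0.3 points.

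**The case against.** The strongest reply is that this hardly matters, and most of it stands.

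- A reader might infer that the protocol uses tablet-count adherence to attribute failures, since Protocol 1.2.2.1.4 describes a breakthrough consistent with non-adherence. That passage rests on undetectable plasma drug levels and does not mention tablet counts. Here a PK sample is taken at each on-treatment visit, and SAP section 8 and listing 16.2.5.3 provide concentrations by subject.
- No planned analysis relates adherence to response. It is not among the SAP 3.4 subgroups, and SAP 6.2.2 splits relapse only by whether study drug was completed. SVR12 and its interval cannot change.
- The by-subject administration and accountability listings run by visit, so a careful reader could reconstruct one subject's record.
- The conditions are narrow. Weeks 4 and 8 are dispensing visits, and a bottle issued at the failing visit is excluded. Continued dosing until confirmation is inferred from the word confirmed in the stopping criteria; the protocol does not state it.
- Read literally, the re-dispensed extra bottle may also be excluded. The SAP does not say. That reading would also drop tablets taken from it before failure, which is a different error.

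A reader might also conclude that every such failure is biased upward. The documents do not support that: with d = 0 there is no inflation, and an unreturned bottle biases the figure down. What the reply does not remove is that the rule, as written, can give a wrong adherence figure.

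**Conclusion.** The point holds as a minor defect in a descriptive rule. For an early stop due to virologic failure, SAP 4.2.2 can overstate adherence by 25 points at Week 8, and by up to 35.7 points (64.3% to 100%) in the Week 4 example. This requires that the subject keeps dosing after the first failing sample and draws on a bottle issued before it. The figures assume up to 14 such tablets and, for Week 8, one bottle dispensed at Week 4.

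Probably zero or one subject would be affected, if transplant recipients fail on treatment about as rarely as the cited phase 3 groups. The primary result is untouched, and the PK and accountability listings offer a check.

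**What to change.** In SAP 4.2.2, use one cut-off date for both terms.

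- Where failure is first met at a scheduled visit, divide tablets taken by that visit's pill count by tablets prescribed to that date. Where it is first met at an unscheduled visit, for which Protocol 6.2.5 does not require a pill count, take both terms to the last dose. Mark in the listing which was used.
- State whether re-dispensing the extra bottle counts as dispensing.
- Show the uncapped percentage in listing 16.2.5.2.

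The cost is a few SAP sentences and minor programming. Protocol 6.2.2 to 6.2.4 already require pill counts at every post-baseline on-treatment visit, and Protocol 5.6 already has subjects bring their study drug, including the extra bottle, to those visits.
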